Amylase and/or lipase elevation, Grade 2	
Amylase and/or lipase $> 1.5\text{--}2.0 \times ULN$:
 
 Continue atezolizumab. Monitor amylase and lipase weekly. For prolonged elevation (e.g., > 3 weeks), consider treatment with corticosteroids equivalent to 10 mg/day oral prednisone. 
Asymptomatic with amylase and/or lipase $> 2.0\text{--}5.0 \times ULN$:
 
 Treat as a Grade 3 event.
Amylase and/or lipase elevation, Grade 3 or 4	
 Withhold atezolizumab for up to 12 weeks after event onset.^a Refer patient to GI specialist. Monitor amylase and lipase every other day. If no improvement, consider treatment with corticosteroids equivalent to 1–2 mg/kg/day oral prednisone. If event resolves to Grade 1 or better, resume atezolizumab.^b If event does not resolve to Grade 1 or better while withholding atezolizumab, permanently discontinue atezolizumab and contact the sponsor.^c For recurrent events, permanently discontinue atezolizumab and contact the sponsor.^c
Immune-mediated pancreatitis, Grade 2 or 3	
 Withhold atezolizumab for up to 12 weeks after event onset.^a Refer patient to GI specialist. Initiate treatment with corticosteroids equivalent to 1–2 mg/kg/day IV methylprednisolone and convert to 1–2 mg/kg/day oral prednisone or equivalent upon improvement. If event resolves to Grade 1 or better, resume atezolizumab.^b If event does not resolve to Grade 1 or better while withholding atezolizumab, permanently discontinue atezolizumab and contact the sponsor.^c

Event	Management
	
 For recurrent events, permanently discontinue atezolizumab and contact the sponsor.^c
Immune-mediated pancreatitis, Grade 4	
 Permanently discontinue atezolizumab.^c Refer patient to GI specialist. Initiate treatment with corticosteroids equivalent to 1–2 mg/kg/day IV methylprednisolone and convert to 1–2 mg/kg/day oral prednisone or equivalent upon improvement. If event does not improve within 48 hours after initiating corticosteroids, consider adding an immunosuppressive agent. If event resolves to Grade 1 or better, taper corticosteroids over \geq 1 month.

GI = gastrointestinal.

^a Atezolizumab may be withheld for a longer period of time (i.e., $>$ 12 weeks after event onset) to allow for corticosteroids (if initiated) to be reduced to the equivalent of \leq 10 mg/day oral prednisone. The acceptable length of the extended period of time must be based on assessment of benefit-risk by the investigator and in alignment with the protocol requirement for duration of treatment and documented by the investigator.

^b If corticosteroids have been initiated, they must be tapered over \geq 1 month to the equivalent of \leq 10 mg/day oral prednisone before atezolizumab can be resumed.

^c Resumption of atezolizumab may be considered in patients who are deriving benefit and have fully recovered from the immune-mediated event. The decision to re-challenge patients with atezolizumab must be based on assessment of benefit-risk by the investigator and in alignment with the protocol requirement for duration of treatment and documented by the investigator.

DERMATOLOGIC EVENTS

Treatment-emergent rash has been associated with atezolizumab. The majority of cases of rash reported with the use of atezolizumab were mild in severity and self-limited, with or without pruritus. A dermatologist should evaluate persistent and/or severe rash or pruritus. A biopsy should be considered unless contraindicated. Management guidelines for dermatologic events are provided in Table 11.

Table 11 Management Guidelines for Dermatologic Events

Event	Management
Dermatologic event, Grade 1	
 Continue atezolizumab. Consider treatment with topical corticosteroids and/or other symptomatic therapy (e.g., antihistamines).
Dermatologic event, Grade 2	
 Continue atezolizumab. Consider patient referral to dermatologist. Initiate treatment with topical corticosteroids. Consider treatment with higher-potency topical corticosteroids if event does not improve. If unresponsive to topical corticosteroids, consider oral prednisone 0.5 mg/kg/day.
Dermatologic event, Grade 3	
 Withhold atezolizumab for up to 12 weeks after event onset.^a Refer patient to dermatologist. Initiate treatment with corticosteroids equivalent to 10 mg/day oral prednisone, increasing dose to 1–2 mg/kg/day if event does not improve within 48–72 hours.

Event	Management
	
 • If event resolves to Grade 1 or better, resume atezolizumab.^b • If event does not resolve to Grade 1 or better while withholding atezolizumab, permanently discontinue atezolizumab.^c
Dermatologic event, Grade 4	
 • Permanently discontinue atezolizumab and contact the sponsor.^c
Stevens-Johnson syndrome or toxic epidermal necrolysis, (any grade)	
Additional guidance for Stevens-Johnson syndrome or toxic epidermal necrolysis:
 
 • Withhold atezolizumab for suspected Stevens-Johnson syndrome or toxic epidermal necrolysis. • Confirm diagnosis by referring patient to a specialist (dermatologist, ophthalmologist or urologist as relevant) for evaluation and, if indicated, biopsy. • Follow the applicable treatment and management guidelines above. • If Stevens-Johnson syndrome or toxic epidermal necrolysis is confirmed, permanently discontinue atezolizumab.

^a Atezolizumab may be withheld for a longer period of time (i.e., > 12 weeks after event onset) to allow for corticosteroids (if initiated) to be reduced to the equivalent of \leq 10 mg/day oral prednisone. The acceptable length of the extended period of time must be based on assessment of benefit-risk by the investigator and in alignment with the protocol requirement for duration of treatment and documented by the investigator.

^b If corticosteroids have been initiated, they must be tapered over \geq 1 month to the equivalent of \leq 10 mg/day oral prednisone before atezolizumab can be resumed.

^c Resumption of atezolizumab may be considered in patients who are deriving benefit and have fully recovered from the immune-mediated event. The decision to re-challenge patients with atezolizumab must be based on assessment of benefit-risk by the investigator and in alignment with the protocol requirement for duration of treatment and documented by the investigator.

NEUROLOGIC DISORDERS

Myasthenia gravis and Guillain-Barré syndrome have been observed with single-agent atezolizumab. Additionally, immune-mediated myelitis and immune-mediated facial paresis have been associated with the use of PD1/PD-L1 immune checkpoint inhibitors as a class of medications. Patients may present with signs and symptoms of sensory and/or motor neuropathy. Diagnostic workup is essential for an accurate characterization to differentiate between alternative etiologies. Management guidelines for neurologic disorders are provided in Table 12.

Table 12 Management Guidelines for Neurologic Disorders

Event	Management
Immune-mediated neuropathy, Grade 1	
 • Continue atezolizumab. • Investigate etiology. • Any cranial nerve disorder (including facial paresis) should be managed as per Grade 2 management guidelines below.
Immune-mediated neuropathy,	
 • Withhold atezolizumab for up to 12 weeks after event onset.^a • Investigate etiology and refer patient to neurologist. • Initiate treatment as per institutional guidelines. • For general immune-mediated neuropathy:

Event	Management
including facial paresis, Grade 2	
 – If event resolves to Grade 1 or better, resume atezolizumab.^b – If event does not resolve to Grade 1 or better while withholding atezolizumab, permanently discontinue atezolizumab and contact the sponsor.^c 
 • For facial paresis: 
 – If event resolves fully, resume atezolizumab^b – If event does not resolve fully while withholding atezolizumab, permanently discontinue atezolizumab and contact the sponsor.^c
Immune-mediated neuropathy, including facial paresis, Grade 3 or 4	
 • Permanently discontinue atezolizumab and contact the sponsor.^c • Refer patient to neurologist • Initiate treatment as per institutional guidelines.
Myasthenia gravis and Guillain-Barré syndrome (any grade)	
 • Permanently discontinue atezolizumab and contact the sponsor.^c • Refer patient to neurologist. • Initiate treatment as per institutional guidelines. • Consider initiation of corticosteroids equivalent to 1–2 mg/kg/day oral or IV prednisone.
Immune-mediated myelitis, Grade 1	
 • Continue atezolizumab unless symptoms worsen or do not improve. • Investigate etiology and refer patient to neurologist.
Immune-mediated myelitis, Grade 2	
 • Permanently discontinue atezolizumab and contact the sponsor. • Investigate etiology and refer patient to a neurologist. • Rule out infection. • Initiate treatment with corticosteroids equivalent to 1-2 mg/kg/day oral prednisone.
Immune-mediated myelitis, Grade 3 or 4	
 • Permanently discontinue atezolizumab and contact the sponsor.^c • Refer patient to neurologist. • Initiate treatment as per institutional guidelines.

^a Atezolizumab may be withheld for a longer period of time (i.e., > 12 weeks after event onset) to allow for corticosteroids (if initiated) to be reduced to the equivalent of ≤ 10 mg/day oral prednisone. The acceptable length of the extended period of time must be based on assessment of benefit-risk by the investigator and in alignment with the protocol requirement for duration of treatment and documented by the investigator.

^b If corticosteroids have been initiated, they must be tapered over ≥ 1 month to the equivalent of ≤ 10 mg/day oral prednisone before atezolizumab can be resumed.

^c Resumption of atezolizumab may be considered in patients who are deriving benefit and have fully recovered from the immune-mediated event. The decision to re-challenge patients with atezolizumab must be based on assessment of benefit-risk by the investigator and in alignment with the protocol requirement for duration of treatment and documented by the investigator.

IMMUNE-MEDIATED MENINGOENCEPHALITIS

Immune-mediated meningoencephalitis is an identified risk associated with the administration of atezolizumab. Immune-mediated meningoencephalitis should be suspected in any patient presenting with signs or symptoms suggestive of meningitis or encephalitis, including, but not limited to, headache, neck pain, confusion, seizure, motor or sensory dysfunction, and altered or depressed level of consciousness. Encephalopathy from metabolic or electrolyte imbalances

needs to be distinguished from potential meningoencephalitis resulting from infection (bacterial, viral, or fungal) or progression of malignancy, or secondary to a paraneoplastic process.

All patients being considered for meningoencephalitis should be urgently evaluated with a CT scan and/or MRI scan of the brain to evaluate for metastasis, inflammation, or edema. If deemed safe by the treating physician, a lumbar puncture should be performed and a neurologist should be consulted.

Patients with signs and symptoms of meningoencephalitis, in the absence of an identified alternate etiology, should be treated according to the guidelines in Table 13.

Table 13 Management Guidelines for Immune-Mediated Meningoencephalitis

Event	Management
Immune-mediated meningoencephalitis, all grades	
 Permanently discontinue atezolizumab and contact the sponsor. Refer patient to neurologist. Initiate treatment with corticosteroids equivalent to 1–2 mg/kg/day IV methylprednisolone and convert to 1–2 mg/kg/day oral prednisone or equivalent upon improvement. If event does not improve within 48 hours after initiating corticosteroids, consider adding an immunosuppressive agent. If event resolves to Grade 1 or better, taper corticosteroids over \geq 1 month.

RENAL EVENTS

Immune-mediated nephritis has been associated with the administration of atezolizumab. Eligible patients must have adequate renal function. Renal function, including serum creatinine, should be monitored throughout study treatment. Patients with abnormal renal function should be evaluated and treated for other more common etiologies (including prerenal and postrenal causes, and concomitant medications such as non-steroidal anti-inflammatory drugs). Refer the patient to a renal specialist if clinically indicated. A renal biopsy may be required to enable a definitive diagnosis and appropriate treatment.

Patients with signs and symptoms of nephritis, in the absence of an identified alternate etiology, should be treated according to the guidelines in Table 14.

Table 14 Management Guidelines for Renal Events

Event	Management
Renal event, Grade 1	
 Continue atezolizumab. Monitor kidney function, including creatinine, closely until values resolve to within normal limits or to baseline values.
Renal event, Grade 2	
 Withhold atezolizumab for up to 12 weeks after event onset.^a Refer patient to renal specialist. Initiate treatment with corticosteroids equivalent to 1–2 mg/kg/day oral prednisone. If event resolves to Grade 1 or better, resume atezolizumab.^b If event does not resolve to Grade 1 or better while withholding atezolizumab, permanently discontinue atezolizumab.^c

Event	Management
Renal event, Grade 3 or 4	
 Permanently discontinue atezolizumab and contact the sponsor. Refer patient to renal specialist and consider renal biopsy. Initiate treatment with corticosteroids equivalent to 1–2 mg/kg/day oral prednisone. If event does not improve within 48 hours after initiating corticosteroids, consider adding an immunosuppressive agent. If event resolves to Grade 1 or better, taper corticosteroids over ≥ 1 month.

^a Atezolizumab may be withheld for a longer period of time (i.e., > 12 weeks after event onset) to allow for corticosteroids (if initiated) to be reduced to the equivalent of ≤ 10 mg/day oral prednisone. The acceptable length of the extended period of time must be based on assessment of benefit-risk by the investigator and in alignment with the protocol requirement for duration of treatment and documented by the investigator.

^b If corticosteroids have been initiated, they must be tapered over ≥ 1 month to the equivalent of ≤ 10 mg/day oral prednisone before atezolizumab can be resumed.

^c Resumption of atezolizumab may be considered in patients who are deriving benefit and have fully recovered from the immune-mediated event. The decision to re-challenge patients with atezolizumab must be based on assessment of benefit-risk by the investigator and in alignment with the protocol requirement for duration of treatment and documented by the investigator.

IMMUNE-MEDIATED MYOSITIS

Myositis or inflammatory myopathies are a group of disorders sharing the common feature of inflammatory muscle injury; dermatomyositis and polymyositis are among the most common disorders. Initial diagnosis is based on clinical (muscle weakness, muscle pain, skin rash in dermatomyositis), biochemical (serum creatine kinase increase), and imaging (electromyography/MRI) features, and is confirmed with a muscle biopsy.

Patients with signs and symptoms of myositis, in the absence of an identified alternate etiology, should be treated according to the guidelines in Table 15.

Table 15 Management Guidelines for Immune-Mediated Myositis

Event	Management
Immune-mediated myositis, Grade 1	
 Continue atezolizumab. Refer patient to rheumatologist or neurologist. Initiate treatment as per institutional guidelines.
Immune-mediated myositis, Grade 2	
 Withhold atezolizumab for up to 12 weeks after event onset^a and contact the sponsor. Refer patient to rheumatologist or neurologist. Initiate treatment as per institutional guidelines. Consider treatment with corticosteroids equivalent to 1–2 mg/kg/day IV methylprednisolone and convert to 1–2 mg/kg/day oral prednisone or equivalent upon improvement. If corticosteroids are initiated and event does not improve within 48 hours after initiating corticosteroids, consider adding an immunosuppressive agent. If event resolves to Grade 1 or better, resume atezolizumab.^b If event does not resolve to Grade 1 or better while withholding atezolizumab, permanently discontinue atezolizumab and contact the sponsor.^c

Event	Management
Immune-mediated myositis, Grade 3	
 Withhold atezolizumab for up to 12 weeks after event onset^a and contact the sponsor. Refer patient to rheumatologist or neurologist. Initiate treatment as per institutional guidelines. Respiratory support may be required in more severe cases. Initiate treatment with corticosteroids equivalent to 1–2 mg/kg/day IV methylprednisolone, or higher-dose bolus if patient is severely compromised (e.g., cardiac or respiratory symptoms, dysphagia, or weakness that severely limits mobility); convert to 1–2 mg/kg/day oral prednisone or equivalent upon improvement. If event does not improve within 48 hours after initiating corticosteroids, consider adding an immunosuppressive agent. If event resolves to Grade 1 or better, resume atezolizumab.^b If event does not resolve to Grade 1 or better while withholding atezolizumab, permanently discontinue atezolizumab and contact the sponsor.^c For recurrent events, treat as a Grade 4 event.
Immune-mediated myositis, Grade 4	
 Permanently discontinue atezolizumab and contact the sponsor.^c Refer patient to rheumatologist or neurologist. Initiate treatment as per institutional guidelines. Respiratory support may be required in more severe cases. Initiate treatment with corticosteroids equivalent to 1–2 mg/kg/day IV methylprednisolone, or higher-dose bolus if patient is severely compromised (e.g., cardiac or respiratory symptoms, dysphagia, or weakness that severely limits mobility); convert to 1–2 mg/kg/day oral prednisone or equivalent upon improvement. If event does not improve within 48 hours after initiating corticosteroids, consider adding an immunosuppressive agent. If event resolves to Grade 1 or better, taper corticosteroids over ≥ 1 month.

^a Atezolizumab may be withheld for a longer period of time (i.e., > 12 weeks after event onset) to allow for corticosteroids (if initiated) to be reduced to the equivalent of ≤ 10 mg/day oral prednisone. The acceptable length of the extended period of time must be based on assessment of benefit-risk by the investigator and in alignment with the protocol requirement for duration of treatment and documented by the investigator.

^b If corticosteroids have been initiated, they must be tapered over ≥ 1 month to the equivalent of ≤ 10 mg/day oral prednisone before atezolizumab can be resumed.

^c Resumption of atezolizumab may be considered in patients who are deriving benefit and have fully recovered from the immune-mediated event. The decision to re-challenge patients with atezolizumab must be based on assessment of benefit-risk by the investigator and in alignment with the protocol requirement for duration of treatment and documented by the investigator.

HEMOPHAGOCYTIC LYMPHOHISTIOCYTOSIS AND MACROPHAGE ACTIVATION SYNDROME

Immune-mediated reactions may involve any organ system and may lead to hemophagocytic lymphohistiocytosis (HLH) and macrophage activation syndrome (MAS).

Patients with suspected HLH should be diagnosed according to published criteria by McClain and Eckstein (2014). A patient should be classified as having HLH if five of the following eight criteria are met:

- Fever $\geq 38.5^{\circ}\text{C}$
- Splenomegaly
- Peripheral blood cytopenia consisting of at least two of the following:
 - Hemoglobin $< 90 \text{ g/L}$ (9 g/dL) ($< 100 \text{ g/L}$ [10 g/dL] for infants < 4 weeks old)
 - Platelet count $< 100 \times 10^9/\text{L}$ ($100,000/\mu\text{L}$)
 - ANC $< 1.0 \times 10^9/\text{L}$ ($1000/\mu\text{L}$)
- Fasting triglycerides $> 2.992 \text{ mmol/L}$ (265 mg/dL) and/or fibrinogen $< 1.5 \text{ g/L}$ (150 mg/dL)
- Hemophagocytosis in bone marrow, spleen, lymph node, or liver
- Low or absent natural killer cell activity
- Ferritin $> 500 \text{ mg/L}$ (500 ng/mL)
- Soluble IL-2 receptor (soluble CD25) elevated ≥ 2 standard deviations above age-adjusted laboratory-specific norms

Patients with suspected MAS should be diagnosed according to published criteria for systemic juvenile idiopathic arthritis by Ravelli et al. (2016). A febrile patient should be classified as having MAS if the following criteria are met:

- Ferritin $> 684 \text{ mg/L}$ (684 ng/mL)
- At least two of the following:
 - Platelet count $\leq 181 \times 10^9/\text{L}$ ($181,000/\mu\text{L}$)
 - AST $\geq 48 \text{ U/L}$
 - Triglycerides $> 1.761 \text{ mmol/L}$ (156 mg/dL)
 - Fibrinogen $\leq 3.6 \text{ g/L}$ (360 mg/dL)

Patients with suspected HLH or MAS should be treated according to the guidelines in Table 16.

Table 16 Management Guidelines for Suspected Hemophagocytic Lymphohistiocytosis or Macrophage Activation Syndrome

Event	Management
Suspected HLH or MAS	
 • Permanently discontinue atezolizumab and contact the sponsor. • Consider patient referral to hematologist. • Initiate supportive care, including intensive care monitoring if indicated per institutional guidelines. • Consider initiation of IV corticosteroids and/or an immunosuppressive agent. • If event does not respond to treatment within 24 hours, contact the sponsor and initiate treatment as appropriate according to published guidelines (La Rosee 2015; Schram and Berliner 2015; La Rosee et al. 2019). • If event resolves to Grade 1 or better, taper corticosteroids over ≥ 1 month.

HLH = hemophagocytic lymphohistiocytosis; MAS = macrophage activation syndrome.

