All participants will undergo a curative-intent surgical resection as defined by SoC. Surgery will occur within 10 weeks of study enrollment and at least two weeks after second dose of neoadjuvant Atezolizumab. The goal of curative intent surgery for regionally metastatic CSCC involves resection to negative margins of the index lesion with the associated at-risk regional lymph nodes as determined by the study physician. An evaluation of tumor status and staging per AJCC guidelines (8th edition) will be performed on all surgical specimen. The pathologist will assess the specimen for pCR and mPR (see 10.1). Pathology assessment will be as per standard of care documentation, including: dimensions of index lesion, total nodal number of lymph nodes removed, total positive node number (and positive nodal levels), any extracapsular extension, any perineural invasion. PD-L1 staining will be performed on a representative section from the largest positive node. Tissue will be formalin fixed and paraffin embedded and banked per standard pathology protocol.

Patients demonstrating pCR at time of surgery:*Adjuvant Treatment*

Patients demonstrating pCR at the time of surgery will not receive any additional adjuvant therapy and will enter surveillance.

Imaging

PET/CT will be performed approximately 12 weeks after surgery.

Follow-up / Surveillance

Patients will be followed in otolaryngology/head and neck surgery and medical oncology clinic every 3 months for 3 years after surgery. Patients will be assessed for treatment-related side effects, cancer recurrence and blood draws performed at the cancer center for biomarkers.

In the setting of suspected clinical or radiographic recurrence per iRECIST criteria, tumor tissue will be collected by biopsy, unless not clinically feasible as assessed and documented by the investigator.

Patients with residual disease at time of surgery:

Patients with residual disease at the time of surgery will receive atezolizumab Q3W x 15 cycles in combination with SoC adjuvant radiation. SoC adjuvant radiation will be initiated greater than 4 weeks and less than 7 weeks after surgery and consists of 6 weeks of radiation therapy with dosimetry determined by pathologic findings at the time of surgery. Recommendations for adjuvant treatment will be determined at a multidisciplinary tumor board where surgical pathology findings will be reviewed. Adjuvant atezolizumab will begin concurrent to adjuvant radiation and continue for 15 cycles.

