4.2 Exclusion Criteria

Patients who meet any of the following criteria will be excluded from study entry:

1. Distant metastatic disease
2. Unresectable disease: As defined by: common or internal carotid artery encasement or involvement of the skull base involvement or pre-vertebral fascia
3. Uncontrolled tumor-related pain
4. Uncontrolled pleural effusion, pericardial effusion, or ascites requiring recurrent drainage procedures (once monthly or more frequently)
 - o Patients with indwelling catheters (e.g., PleurX®) are allowed.
5. Uncontrolled (ionized calcium > 1.5 mmol/L, calcium > 12 mg/dL or corrected serum calcium $> ULN$) or symptomatic hypercalcemia
6. Active or history of autoimmune disease or immune deficiency (see Section 15.9), including, but not limited to, myasthenia gravis, myositis, autoimmune hepatitis, systemic lupus erythematosus, rheumatoid arthritis, inflammatory bowel disease, antiphospholipid antibody syndrome, Wegener granulomatosis, Sjögren syndrome, Guillain-Barré syndrome, or multiple sclerosis, with the following exceptions:
 - o Patients with a history of autoimmune-related hypothyroidism who are on thyroid-replacement hormone are eligible for the study.
 - o Patients with controlled Type 1 diabetes mellitus who are on an insulin regimen are eligible for the study.
 - o Patients with eczema, psoriasis, lichen simplex chronicus, or vitiligo with dermatologic manifestations only (e.g., patients with psoriatic arthritis are excluded) are eligible for the study provided all of following conditions are met:
 - Rash must cover $< 10\%$ of body surface area
 - Disease is well controlled at baseline and requires only low-potency topical corticosteroids
 - No occurrence of acute exacerbations of the underlying condition requiring psoralen plus ultraviolet A radiation, methotrexate, retinoids, biologic agents, oral calcineurin inhibitors, or high-potency or oral corticosteroids within the previous 12 months.
 - o Any history of idiopathic pulmonary fibrosis, organizing pneumonia (e.g., bronchiolitis obliterans), drug-induced pneumonitis, or idiopathic pneumonitis, or evidence of active pneumonitis on screening chest computed tomography (CT) scan. History of radiation pneumonitis in the radiation field (fibrosis) is permitted
7. Known active tuberculosis.

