The investigator should consider the benefit-risk balance a given patient may be experiencing prior to further administration of atezolizumab. In patients who have met the criteria for permanent discontinuation, resumption of atezolizumab may be considered if the patient is deriving benefit and has fully recovered from the immune-mediated event. The decision to rechallenge patients with atezolizumab should be based on investigator's assessment of benefit-risk and documented by the investigator (or appropriate delegate).

DOSE MODIFICATIONS

There will be no dose modifications for atezolizumab in this study.

TREATMENT INTERRUPTION

Atezolizumab treatment may be temporarily suspended in patients experiencing toxicity considered to be related to study treatment. If corticosteroids are initiated for treatment of the toxicity, they must be tapered over ≥ 1 month to the equivalent of ≤ 10 mg/day oral prednisone before atezolizumab can be resumed

MANAGEMENT GUIDELINES

Guidelines for managing patients who experience selected adverse events are provided in the following sections. Management guidelines are presented by adverse event severity based on the National Cancer Institute Common Terminology Criteria for Adverse Events (NCI CTCAE).

PULMONARY EVENTS

Pulmonary events may present as new or worsening cough, chest pain, fever, dyspnea, fatigue, hypoxia, pneumonitis, and pulmonary infiltrates. Patients will be assessed for pulmonary signs and symptoms throughout the study and will have computed tomography (CT) scans of the chest performed at every tumor assessment.

All pulmonary events should be thoroughly evaluated for other commonly reported etiologies, such as pneumonia or other infection, lymphangitic carcinomatosis, pulmonary embolism, heart failure, chronic obstructive pulmonary disease, or pulmonary hypertension. Management guidelines for pulmonary events are provided in Table 3.

Table 3. Management Guidelines for Pulmonary Events, Including Pneumonitis

Event	Management
Pulmonary event, Grade 1	
Continue atezolizumab and monitor closely.Re-evaluate on serial imaging.Consider patient referral to pulmonary specialist.For Grade 1 pneumonitis, consider withholding atezolizumab

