Pulmonary event, Grade 2	
Withhold atezolizumab for up to 12 weeks after event onset.^aRefer patient to pulmonary and infectious disease specialists and consider bronchoscopy or BAL with or without transbronchial biopsy.Initiate treatment with corticosteroids equivalent to 1-2 mg/kg/day oral prednisone.If event resolves to Grade 1 or better, resume atezolizumab.^bIf event does not resolve to Grade 1 or better while withholding atezolizumab, permanently discontinue atezolizumab.^{c, d}For recurrent events or events with no improvement after 48-72 hours of corticosteroids, treat as a Grade 3 or 4 event.

Event	Management
Pulmonary event, Grade 3 or 4	
 Permanently discontinue atezolizumab and contact the sponsor.^c Oral or IV broad-spectrum antibiotics should be administered in parallel to the immunosuppressive treatment Bronchoscopy or BAL with or without transbronchial biopsy is recommended. Initiate treatment with corticosteroids equivalent to 1-2 mg/kg/day IV methylprednisolone. If event does not improve within 48 hours after initiating corticosteroids, consider adding an immunosuppressive agent. If event resolves to Grade 1 or better, taper corticosteroids over ≥ 1 month.

BAL = bronchoscopic alveolar lavage.

^a Atezolizumab may be withheld for a longer period of time (i.e., > 12 weeks after event onset) to allow for corticosteroids (if initiated) to be reduced to the equivalent of ≤ 10 mg/day oral prednisone. The acceptable length of the extended period of time must be based on assessment of benefit-risk by the investigator and in alignment with the protocol requirement for duration of treatment and documented by the investigator.

^b If corticosteroids have been initiated, they must be tapered over ≥ 1 month to the equivalent of ≤ 10 mg/day oral prednisone before atezolizumab can be resumed.

^c Resumption of atezolizumab may be considered in patients who are deriving benefit and have fully recovered from the immune-mediated event. The decision to re-challenge patients with atezolizumab should be based on investigator's assessment of benefit-risk and documented by the investigator (or appropriate delegate). The sponsor may be reached at [contact] (also see page 1 for the sponsor's contact information).

^d In case of pneumonitis, atezolizumab should not be resumed after permanent discontinuation.

HEPATIC EVENTS

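### Table 3 marks the bar on resuming atezolizumab after pneumonitis on the unresolved Grade 2 line but not on the Grade 3 or 4 line (minor internal inconsistency)

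*Combined protocol and SAP*

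**What the plan says.** Table 3 in Section 7.4 is titled "Management Guidelines for Pulmonary Events, Including Pneumonitis", so one set of rows governs pneumonitis and all other pulmonary events. Two of its lines end in permanent discontinuation.

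- **Grade 2, not resolved to Grade 1 or better while drug is withheld.** This line carries markers c and d.
- **Grade 3 or 4.** This line reads "Permanently discontinue atezolizumab and contact the sponsor.^c" and carries marker c only.

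The Grade 2 row also contains an escalation rule: "For recurrent events or events with no improvement after 48-72 hours of corticosteroids, treat as a Grade 3 or 4 event".

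Footnote c opens the way back: "Resumption of atezolizumab may be considered in patients who are deriving benefit and have fully recovered from the immune-mediated event". It leaves the decision to the investigator's documented benefit-risk assessment. Footnote d closes the way back for one diagnosis: "In case of pneumonitis, atezolizumab should not be resumed after permanent discontinuation".

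**The concern.** Footnote d is the only statement in Section 7.4 that rules out resuming atezolizumab after permanent discontinuation for pneumonitis. An investigator managing a Grade 3 case will go to the Grade 3 or 4 row and follow its marker. That leads to footnote c, which allows re-challenge to be considered, and not to footnote d.

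This is an operative dosing rule. It bears on whether a patient who has recovered from Grade 3 or 4 pneumonitis, or from Grade 2 pneumonitis that recurred or did not improve on steroids, may be given atezolizumab again. The exposure could be long, because "Patients with residual disease at the time of surgery will receive atezolizumab Q3W x 15 cycles in combination with SoC adjuvant radiation".

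**Working it through.** There is no stated figure to reproduce. The check is a side-by-side reading of Table 3, followed by a count of the doses the rule could affect.

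**Markers on the permanent-discontinuation lines**

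| Line in Table 3 | Who reaches it | c (resumption may be considered) | d (no resumption in pneumonitis) |
|---|---|---|---|
| Grade 2, unresolved | Grade 2 events that do not settle while drug is withheld | yes | yes |
| Grade 3 or 4 | Grade 3 or 4 events, plus Grade 2 events that recur or do not improve in 48-72 hours on steroids | yes | no |

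Footnote c is on 2 of 2 lines and footnote d on 1 of 2. One consequence is that two Grade 2 pneumonitis cases can meet different markers. If the event improves on steroids but never reaches Grade 1, it ends on the line marked c, d. If it does not improve within 48-72 hours, it moves to the line marked c.

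**Does the marker carry meaning?** Section 7.4 omits c on several permanent-discontinuation lines: cardiac events (Table 8), confirmed Stevens-Johnson syndrome or toxic epidermal necrolysis (Table 11), meningoencephalitis (Table 13), Grade 3 or 4 renal events (Table 14), and suspected HLH or MAS (Table 16). A reader therefore has some reason to take c as a signal that re-challenge is open.

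**Does other text settle it?** Not fully. The general paragraph on resumption in Section 7.4, just before the dose-modification statement, allows resumption after permanent discontinuation and names no exception for pneumonitis. The sentence introducing the general recommendations confines them to events without their own subsection, which points towards Table 3 governing. The resumption paragraph does not repeat that limit.

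**Doses that could turn on the rule** (Section 3.1: 2 neoadjuvant doses; 15 adjuvant doses with residual disease; none with pCR)

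- Planned total with residual disease: 2 + 15 = 17.
- Event after the first dose: 17 - 1 = 16 doses remain. This is the ceiling, because a rule on resumption cannot govern the first dose.
- Event after both neoadjuvant doses, residual disease: 17 - 2 = 15 remain.
- Event after both neoadjuvant doses, pCR: 0 remain.

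Section 5.3 sends a patient who discontinues in the neoadjuvant phase on to surgery, so the second neoadjuvant dose would normally be skipped. That makes 15 a more realistic maximum than 16.

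**The case against.** The strongest reply is that the text of footnote d already covers the case. It names no grade and no row, it follows c directly in the same footnotes, and the Grade 3 or 4 line is itself a permanent-discontinuation line. Footnote c must appear there for pulmonary events other than pneumonitis, and a specific note qualifies a general one. Marker placement in Section 7.4 is also not uniformly careful: in Table 12, Grade 2 myelitis lacks c while Grade 3 or 4 myelitis has it. This argument stands as far as intent goes. It makes a drafting slip much more likely than a deliberate permission. It does not remove the problem for a reader who follows the row's own marker.

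The safeguards also count. Footnote c requires benefit, full recovery and a documented decision, the Grade 3 or 4 line requires contact with the sponsor, and Section 5.3 directs patients who discontinue to standard care. These lower the severity. They do not replace d, because a patient who has recovered from pneumonitis could meet every condition in c.

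Three stronger readings are tempting, and the documents do not support them.

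- **A reader might infer that the protocol authorises re-challenge after severe pneumonitis.** It does not say so; d's ungraded wording points the other way.
- **A reader might infer support from the entry criteria.** Section 4.2 lists "Any history of idiopathic pulmonary fibrosis, organizing pneumonia (e.g., bronchiolitis obliterans), drug-induced pneumonitis, or idiopathic pneumonitis" and adds that "History of radiation pneumonitis in the radiation field (fibrosis) is permitted". But Table 3 openly allows resumption after Grade 2 pneumonitis that resolves to Grade 1 or better, so an entry exclusion does not set the on-study rule. The item is also printed among the exceptions to criterion 6.
- **A reader might infer that the table is stricter on the less serious course.** A Grade 2 event that stays unresolved while drug is withheld for up to 12 weeks is a persistent course, and not plainly the less serious one.

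**Conclusion.** The inconsistency is real and minor. Footnote d is marked on one of the two permanent-discontinuation lines in Table 3, while its wording fits both. Followed by its markers, the table leaves re-challenge open after Grade 3 or 4 pneumonitis and after Grade 2 events escalated to that row. Followed by the wording of d, it bars re-challenge in all of them. The second reading is probably the intended one.

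The ceiling of 16 doses describes exposure that could turn on the rule; it does not measure risk. The documents give no pneumonitis incidence, so no frequency is claimed. The pCR analysis, error rates and sample size are unaffected.

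The conclusion assumes that the superscripts were read correctly from the PDF. Both c, d and c were captured on their respective lines and nothing suggests a loss, but the point rests on a single letter.

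**What to change.** Check the source PDF for a lost superscript on the Grade 3 or 4 line of Table 3. If d is absent there too, change the marker from c to c, d. This is the pairing already used on the unresolved Grade 2 line: c continues to apply to other pulmonary events, and d bars resumption after permanent discontinuation for pneumonitis at every grade.

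Optionally, add a short clause to the general resumption paragraph in Section 7.4 saying that the event-specific tables take precedence. The scope sentence already points that way, so this adds little.

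The cost is one footnote letter, with no new procedures, patients or data.
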